4.3 Dispensing Study Products During the Trial (after Randomization)

- 1) At each clinic visit, record the number of capsules consumed since the last study visit on the Compliance Calculation Form **[Form 26]**. The DCC will use these data to replace the appropriate number of study products in the participant's study product storage container.
- 2) From the study product storage area containing study products for participants that have already been randomized, which are sorted by the participant study ID, locate the participant's stored products.
- 3) From the participant's storage containers, obtain the same number of bottles of capsules that were consumed since the last visit (recorded on the Compliance Calculation Form **[Form 26]**).

5.0

COMPLIANCE AND DROPOUT

5.1 Clinic Appointments

Overall compliance will be determined by the number of missed regularly scheduled clinic visits. The visit limit window will be ± 14 days of the actual clinic visit date. Out of window visits will also be calculated.

5.2 Medication

Compliance with active nattokinase and nattokinase placebo [**FORM 26**] will be evaluated by capsule count. Compliance will be defined as $\geq 80\%$ of capsules consumed.

Percentage of active nattokinase and nattokinase placebo consumed will be determined by the formula:

$$\frac{\text{TCD} - \text{TCR}}{\text{D} \times \text{A}} \times 100,$$

where TCD=total number of capsules dispensed; TCR=total number of capsules returned; D=number of capsules to be taken each day; and, A=actual number of days since last visit.

5.3 Dropouts

Participants who do not want to continue to participate in the study or to take the study product will be urged to complete all clinic visits and to be followed for cardiovascular disease events as well as undergo the remainder of carotid artery ultrasound examinations and other studies including those for the secondary end points. A participant who stops taking the study product but continues to attend clinic visits and to complete ultrasound examinations and other secondary end points will be termed a “medication termination.” A participant who ceases participation and does not attend clinic visits will be termed a “dropout.”

All dropouts and reasons for terminating the study or terminating use of study product will be recorded on the Medication Termination/Dropout Form [**FORM 27**].

6.0

CLINICAL EVENTS AND DEFINITIONS

6.1 Overview

Participants on trial will continue with their usual source of medical care. Laboratory abnormalities and other abnormal findings detected at the ARU Research Clinic will be immediately brought to the attention of the principal investigator and with permission from the participant, the participant's private physician will be notified by letter and/or telephone depending upon the urgency of the abnormality detected. Participants who discontinue the study product will be urged to complete all clinic visits and be followed for CVD events as well as undergo the remainder of carotid artery ultrasound scans and other studies including those for the secondary end point. All laboratory and clinical abnormalities requiring referral to or follow-up by a private physician will be recorded in the participant's clinic chart.

6.2 Cardiovascular Events

Participants who develop angina pectoris, decreased exercise tolerance, myocardial infarction, or other cardiovascular events will receive care for this from a private physician. Participants will be referred to their private physician in accordance with the standard practice of medicine but continue on the study protocol unless contraindicated. Analysis of cardiovascular events will include all randomized participants and will be based on documentation from written medical records. Documentation of myocardial infarction and unstable angina must fulfill criteria outlined below. Coronary revascularization (CABG and PTCA) will be considered a major cardiovascular clinical event. Angina pectoris will be evaluated by criteria from the Rose Questionnaire [**FORM 10**]. All cardiovascular events are reported on the Study Event Record [**FORM 28**].

6.3 Ischemic Heart Disease Definitions

6.3.1 Myocardial Infarction

Symptoms:

Pain or discomfort occurring in the anterior chest, back, epigastrium, jaw, neck, left shoulder, elbow, forearm, or wrist, which the attending physician believes to be consistent with a myocardial infarction (MI). These symptom criteria will not apply when there is cardiovascular collapse resulting in unconsciousness or if infarction occurs under general anesthesia for non-cardiac surgery. In addition, new onset or worsening dyspnea may be a symptom of MI if it is associated with other findings of myocardial necrosis (see below).

Serum enzymes:

The following creatine kinase (CK), creatine kinase-muscle/brain (CK-MB), troponin, aspartate amino transferase (AST), or lactic acid dehydrogenase (LDH) enzyme changes are defined as diagnostic of MI if they occur independently of conditions known to be associated with elevated levels. These conditions include but are not limited to rhabdomyolysis, muscle trauma seizures and muscular dystrophy.

- a) In a Q-wave MI there must be:
 - 1) An increase of CK two times or greater than the upper limit of normal for the laboratory where the level was determined, or
 - 2) A positive CK-MB fraction with a 50% rise of total CK over baseline or a 50% fall in total CK relative to peak CK of any levels occurring within 48 hours of the onset of clinical symptoms, or
 - 3) An increase of troponin to a level considered consistent with myocardial necrosis for the laboratory where the level is determined, or
 - 4) Elevations of AST or LDH three times or greater than the upper limit of normal for the laboratory where the level was determined occurring within 72 hours of the onset of clinical symptoms.
- b) In a non-Q wave MI there must be:
 - 1) An increase of CK two times or greater than the upper limit of normal for the laboratory where the level was determined, or
 - 2) A positive CK-MB fraction with a 50% rise of total CK over baseline or a 50% fall in total CK relative to peak CK of any levels occurring within 48 hours of the onset of clinical symptoms.
 - 3) An increase of troponin to a level considered consistent with myocardial necrosis for the laboratory where the level is determined.
- c) With clinical symptoms and enzyme changes only:
 - 1) The CK must rise two times or greater than the upper limit of normal for the laboratory where the level is determined and the CK-MB fraction must be positive, or
 - 2) An increase of troponin to a level considered consistent with myocardial necrosis for the laboratory where the level is determined

Electrocardiogram:

- a) Q-wave MI: On a standard 12-lead ECG, new Q or QS waves with:
 - a duration > 30 msec, and
 - an amplitude > 0.1 mV
 - demonstrated in:
 - two of the three leads, II, III, or avF, or
 - two adjacent leads of V1, V2, V3, V4, V5, V6, I, or avL, or growth of R waves in leads V1 or V2 with ST-T wave changes.
- b) Non-Q-wave MI: On a standard 12-lead ECG, new T-wave inversions in:
 - two of the three leads, II, III, avF, or
 - two adjacent leads of V1, V2, V3, V4, V5, V6, I, or avL which persist for >72 hours

Therefore, three ECGs will be required to make the diagnosis of a non-Q-wave MI:

 - 1) An old ECG demonstrating no T-wave inversions,
 - 2) An ECG showing new T-wave inversions, and
 - 3) An ECG taken >72 hours after development of the new T-wave inversions demonstrating persistence.

Criteria for diagnosis of MI:

A participant must have one of the following combinations of symptoms, enzyme changes and ECG changes described above to meet the criteria for the diagnosis of a MI:

- a) Clinical symptoms, an ECG consistent with a Q-wave MI, and positive enzyme changes (for a Q-wave MI).
- b) Clinical symptoms, an ECG consistent with a non-Q-wave MI, and positive enzyme changes (for a non-Q-wave MI).
- c) With a negative ECG, clinical symptoms and positive enzyme changes (described above under serum enzymes, part c).
- d) With no symptoms and no enzyme changes, a Q-wave MI is confirmed if Q or QS waves meeting the ECG criteria above appear on serial ECGs. (In the absence of symptoms and enzyme changes, a non-Q-wave MI cannot be made).
- e) With no enzyme changes, clinical symptoms and Q or QS waves meeting the ECG criteria above for a Q-wave MI appear on serial ECGs.
- f) With no enzyme changes, clinical symptoms and T-wave inversions meeting the ECG criteria above for a non-Q-wave MI appear on serial ECGs.

All non-fatal myocardial infarctions will be confirmed and recorded on the Confirmation of New Non-fatal Myocardial Infarction Form **[FORM 29]** as well as reported on the Study Event Record **[FORM 28]**.

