6.3.2 Unstable Angina/Chest Pain

Transient ECG changes consisting of S-T segment elevation, S-T depression, T-wave changes, or a combination of these, must be documented during episodes of clinical symptoms as described above. These abnormalities must revert toward the control pattern after relief of pain and within 24 hours. There must be no ECG evidence of evolving MI (i.e., pathologic Q or QS waves). MI must be ruled out by serial serum enzyme studies.

Hospitalization for chest pain or other clinical symptoms considered to be anginal equivalents but not meeting the above criteria for unstable angina will be considered chest pain.

All unstable angina and chest pain events will be confirmed and recorded on the Confirmation of Unstable Angina/Chest Pain Form **[FORM 30]** as well as reported on the Study Event Record **[FORM 28]**.

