9.6.5.4 Analysis of Clinical Events, Adverse Experiences, and Safety Measures

The following clinical events will be tabulated and compared between treatment groups using chi-square or Fisher's exact methods:

- 1) Major cardiovascular events: fatal/nonfatal MI, sudden coronary death, hospitalization for unstable angina, and revascularization procedures (CABG and PTCA).
- 2) Major cerebrovascular events: TIA, RIND, CVA.
- 3) Deep vein thrombosis.
- 4) Pulmonary thromboembolism.
- 5) Incident cancers.
- 6) All cause mortality and cause-specific mortality, including cardiovascular, cerebrovascular, peripheral vascular, cancer, other medical, and non-medical and non-coronary mortality.
- 7) The treatment groups will also be compared for standard clinical and laboratory safety tests.

In the analysis of laboratory safety variables, treatment groups will be compared with regard to proportions of participants with clinically meaningful changes (either increase or decreases from normal range). Analyses of these data will be done using a chi-square test or Mantel-Haenszel test that allows for stratification, as appropriate.

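### The closed MI list in Section 6.3.1 leaves out new Q waves with positive enzymes and no qualifying symptom, and a narrow band of T-wave inversion falls between MI and unstable angina

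*Combined protocol and SAP*

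**What the plan says.** Section 6.2 makes the definitions binding: "Documentation of myocardial infarction and unstable angina must fulfill criteria outlined below". Section 6.3.1 then closes the MI list: "A participant must have one of the following combinations of symptoms, enzyme changes and ECG changes described above to meet the criteria". Six items follow. Three concern new Q or QS waves:

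- (a) requires symptoms, a Q-wave ECG and positive enzymes.
- (d) reads "With no symptoms and no enzyme changes, a Q-wave MI is confirmed if Q or QS waves meeting the ECG criteria above appear".
- (e) reads "With no enzyme changes, clinical symptoms and Q or QS waves meeting the ECG criteria above for a Q-wave MI appear on serial ECGs".

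For T-wave inversion without enzyme changes, item (f) reads "With no enzyme changes, clinical symptoms and T-wave inversions meeting the ECG criteria above for a non-Q-wave MI appear on serial ECGs". The ECG criterion it points to requires the inversion to last more than 72 hours.

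Section 6.3.2 defines unstable angina by transient ST or T changes during symptoms, with MI ruled out by enzymes, and adds: "These abnormalities must revert toward the control pattern after relief of pain and within 24 hours". A hospitalized episode that fails this definition is classed as chest pain and recorded on Form 30.

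MI and hospitalized unstable angina are among the major cardiovascular events in the safety report to the monitoring board (Section 9.5.2.4) and in the between-arm comparison by chi-square or Fisher's exact test (Section 9.6.5.4). Chest pain is in neither list of major events.

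**The concern.** An event definition should not lose a diagnosis when the evidence for it gets stronger. Item (d) accepts Q waves with neither symptoms nor enzyme changes. If positive enzymes are added to the same ECG, (d) no longer applies, and no other item takes the case unless a symptom is present. Because the criteria are binding and the list is closed, a confirmer who follows the text cannot record an MI.

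The second gap is of the same kind but weaker. A symptomatic, enzyme-negative T-wave inversion can be unstable angina if it reverts early and an MI if it lasts long enough, yet one band in between is neither.

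What is at stake is the classification of a few safety events: whether they count as major cardiovascular events in the monitoring board's table and in the final comparison, or appear elsewhere.

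**Working it through.** The plan gives no figure to reproduce on this point. The check is to lay out the combinations and read off the category that each receives.

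**Inputs.** Items (a) to (f), the enzyme definitions, the ECG criteria and the symptom paragraph in Section 6.3.1; the unstable-angina and chest-pain rules in Section 6.3.2; the event lists in Sections 9.5.2.4 and 9.6.5.4.

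**Step 1: new Q or QS waves.**

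| Symptoms | Enzymes | Category |
|---|---|---|
| yes | positive | MI, item (a) |
| yes | no change | MI, item (e) |
| no | no change | MI, item (d) |
| no | positive | none |

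Three of the four cells count. In the fourth, (a), (b) and (c) fail because each needs symptoms; (d) fails because it requires no enzyme changes; (e) and (f) fail on both grounds. Item (c) fails for lack of symptoms, so the result does not depend on how its negative-ECG condition is read.

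**Step 2: how wide the empty cell is.** The symptom paragraph narrows it in three ways. New or worse dyspnea may count as a symptom when other findings of necrosis are present, and positive enzymes are such a finding. The symptom requirement is also waived for collapse with loss of consciousness and for infarction under general anesthesia in non-cardiac surgery. Those cases can qualify under (a). The empty cell is therefore a participant with no pain at a listed site, no dyspnea counted as a symptom, no such collapse and no such anesthesia.

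The cell can still be reached. Of the four enzyme criteria for a Q-wave MI, the CK-MB and the AST/LDH criteria refer to the onset of symptoms, but the twofold CK rise and the troponin criterion do not. The trial's own chemistry panel (Section 7.11.1) contains neither CK nor troponin, so these results would have to come from outside medical records. That makes the case rare.

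**Step 3: symptomatic T-wave inversion without enzyme changes.**

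| Course of the inversion | Category |
|---|---|
| reverts toward the control pattern within 24 hours | unstable angina, if the other conditions of 6.3.2 hold |
| no reversion begun by 24 hours, gone by 72 hours | neither; chest pain if hospitalized, otherwise no category |
| persists beyond 72 hours | MI, item (f) |

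In the middle row, (a) to (c) fail for lack of enzymes, (d) and (e) for lack of Q waves, and (f) for lack of persistence. Total duration is not the criterion. Section 6.3.2 asks only for reversion toward the control pattern, so an inversion that starts to revert at 12 hours and clears at 50 hours meets its timing rule.

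ST elevation or depression that has not begun to revert by 24 hours, with symptoms and without enzyme changes or Q waves, is in a similar position. The non-Q-wave criterion names only T-wave inversion, so (f) does not take these cases at any duration.

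**Step 4: where the cases go.** The Step 1 case is not an MI for Sections 9.5.2.4 and 9.6.5.4. The middle row of Step 3 is at most chest pain, which neither section lists as a major event.

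**The case against.** The strongest reply is that (d) plainly means even with no symptoms and no enzyme changes, so that a case with enzymes is included all the more. That is probably the intention, but it is not what the list says. Items (d), (e) and (f) each state the enzyme status, and if Q waves sufficed whatever the enzymes and symptoms, (a) and (e) would be unnecessary.

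Several stronger readings are tempting, and the documents do not support them.

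- *Every painless Q-wave MI with positive enzymes is lost.* This is wrong, because of the dyspnea provision and the two waivers in Section 6.3.1.
- *Every ECG change lasting 24 to 72 hours falls between the rules.* This is wrong, because Section 6.3.2 requires reversion toward the control pattern within 24 hours, not full resolution. Hospitalized cases that fail also have an explicit category, chest pain. Preferring a broader unstable-angina class would be a matter of choice; what stands is that the non-hospitalized remainder has no category and that shorter and longer courses both count.
- *The events vanish from safety review.* They do not. Section 6.2 puts all cardiovascular events on Form 28, Section 6.12.2 sends all clinical events to the monitoring board, and Section 9.5.2.4 has a row for other adverse events. A misclassified event changes row, and revascularization counts in its own right.
- *The comparison of arms is biased or its result is likely to turn on this.* The same definitions apply in both arms of a blinded trial. Assuming 120 per arm, Fisher's two-sided p is 2 × C(120,5)/C(240,5) ≈ 0.06 for a 5–0 split and 2 × C(120,6)/C(240,6) ≈ 0.03 for 6–0. With five or fewer events, no allocation reaches 0.05.

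**Conclusion.** The omission in the MI list holds on the text: one of four Q-wave cells has no category, and it carries more evidence of infarction than the symptom-free cell that counts. The second gap holds only for symptomatic, enzyme-negative T-wave inversion that has not begun to revert by 24 hours and is gone by 72 hours.

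The effect is small. It concerns the classification of safety events only; carotid intima-media thickness, arterial stiffness and cognition are untouched. Both cases are expected to be rare. The documents give no coronary event rate and nothing on how often these combinations arise, so any percentage of events affected would be invented. The conclusion assumes that confirmers apply the binding criteria literally. If in practice they read (d) as including positive enzymes, the first gap has no effect on the data, but the text should still say so.

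**What to change.** 1. Reword the opening of item (d) to: *With no symptoms, with or without enzyme changes, a Q-wave MI is confirmed if…*, leaving the rest of the item as it is. This fills the empty cell and moves no other.

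2. Reconcile Sections 6.3.1 and 6.3.2 so that every combination of symptoms, enzymes and ECG course, including ST change that does not revert early, maps to exactly one category, and say where non-hospitalized episodes go. Which category takes the band between the two rules is a clinical choice for the sponsor. Simply deleting the 24-hour limit is not a solution: an inversion that persists beyond 72 hours and later reverts would then meet both item (f) and unstable angina.

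The cost is one phrase, a short reconciling rule and matching text on Forms 29 and 30. If events have already been confirmed, Forms 28 to 30 should be re-read against the new wording by staff who do not know the treatment assignment.

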6.3.2 Unstable Angina/Chest Pain

Transient ECG changes consisting of S-T segment elevation, S-T depression, T-wave changes, or a combination of these, must be documented during episodes of clinical symptoms as described above. These abnormalities must revert toward the control pattern after relief of pain and within 24 hours. There must be no ECG evidence of evolving MI (i.e., pathologic Q or QS waves). MI must be ruled out by serial serum enzyme studies.

Hospitalization for chest pain or other clinical symptoms considered to be anginal equivalents but not meeting the above criteria for unstable angina will be considered chest pain.

All unstable angina and chest pain events will be confirmed and recorded on the Confirmation of Unstable Angina/Chest Pain Form **[FORM 30]** as well as reported on the Study Event Record **[FORM 28]**.

6.4 Cerebrovascular Events

Transient ischemic attacks, reversible ischemic neurologic deficits, and cerebrovascular accidents will be documented from written medical records and must fulfill the criteria outlined below. Subjects with these cerebrovascular events will continue on the study protocol unless contraindicated. Analysis of cerebrovascular events will include all randomized subjects.

All cerebrovascular events are reported on the Study Event Record **[FORM 28]**.

6.5 Cerebrovascular Disease Definitions

Occurrence of transient ischemic attacks, reversible ischemic neurologic deficits, and cerebrovascular accidents will be documented by written medical records and must fulfill the following criteria:

6.5.1 Transient Ischemic Attack

A sudden focal neurological deficit that completely resolves within 24 hours.

All transient ischemic attack events will be confirmed and recorded on the Confirmation of Transient Ischemic Attack Form **[FORM 31]** as well as reported on the Study Event Record **[FORM 28]**.

6.5.2 Reversible Ischemic Neurologic Deficit

A focal neurological deficit that persists for more than 24 hours but in which complete neurological recovery occurs within 2 weeks.

All reversible ischemic neurologic deficit events will be confirmed and recorded on the Confirmation of Reversible Ischemic Neurologic Deficit Form **[FORM 32]** as well as reported on the Study Event Record **[FORM 28]**.

6.5.3 Cerebrovascular Accident

A focal neurological deficit that permanently persists after the acute event.

All cerebrovascular accident events will be confirmed and recorded on the Confirmation of Cerebrovascular Accident Form **[FORM 33]** as well as reported on the Study Event Record **[FORM 28]**.

6.6 Peripheral Vascular Events

Aortic aneurysms and peripheral vascular disease requiring surgical or intravascular intervention will be considered major events documented by written medical records. Claudication will be considered a symptom and evaluated by criteria defined below. Participants will continue on study protocol unless health care requirements for these events preclude this. Analysis of major peripheral vascular events will include all randomized participants.

All peripheral vascular disease events requiring surgical or intravascular intervention will be confirmed and recorded on the Confirmation of Peripheral Vascular Disease Form **[FORM 34]** as well as reported on the Study Event Record **[FORM 28]**.

6.7 Peripheral Vascular Disease Definitions

Aortic aneurysms and peripheral vascular disease requiring surgical or revascularization intervention will be considered proof of disease. Participants will be considered to have claudication if they have reproducible pain or weakness in the calf or foot after walking a fixed distance if the pain subsides within a few minutes after stopping **[FORM 11]**.

6.8 Cancer Events

The occurrence of cancer will be documented by medical records and pathology reports. Participants will continue in the study unless contraindicated. Analysis of cancer events will include all randomized participants.

All cancer events will be confirmed and recorded on the Confirmation of Cancer Form **[FORM 35]** as well as reported on the Study Event Record **[FORM 28]**.

